1. INTRODUCTION

The purpose of this document is to provide details on study populations and on how the variables will be derived, how missing data will be handled as well as details on statistical methods to be used to analyze the safety and efficacy data.

The document may evolve over time, for example, to reflect the requirements of protocol amendments or regulatory requests. However, the final SAP will be finalized, approved by the Protocol Chairs, and placed on file before the database is locked.

2. STUDY OBJECTIVES AND ENDPOINTS

2.1. Study Objectives

2.1.1. Primary Objective

1. Evaluate the effectiveness of doxycycline post-exposure prophylaxis (PEP) to reduce STI infections in two populations: a) MSM/TGW living with HIV and b) MSM/TGW taking HIV PrEP.
2. Investigate the impact of doxycycline PEP on development of culture-based tetracycline (TCN) resistance in *N. gonorrhoeae* (GC) and among nasopharyngeal carriers of *S. aureus*.

2.1.2. Secondary Objective

1. Assess the safety, tolerability, and acceptability of doxycycline PEP
2. Investigate the impact of doxycycline PEP on development molecular markers of tetracycline (TCN) resistance *C. trachomatis* (CT), and *T. pallidum* (syphilis).
3. Evaluate the development of phenotypic tetracycline resistance among nasopharyngeal carriers of commensal *Neisseria* species.
4. Measure the proportion of sex acts which are covered by doxycycline PEP
5. Assess the effect of doxycycline PEP on the gut resistome through measuring the abundance of tetracycline resistance genes in a subset of 50 MSM living with HIV and 50 MSM/TGW on PrEP assigned to receive doxycycline PEP as well as rectal swabs from all participants, stored for future evaluation.

2.2. Study Endpoints

2.2.1. Primary Endpoints

2.2.1.1. Effectiveness of doxycycline

The primary endpoint is any of the following STI endpoints post-enrollment:

- Documented positive GC by NAAT
- Documented positive CT by NAAT
- Early syphilis infection based on four-fold increase in non-treponemal titers or positive darkfield on exudate from a lesion.

STIs are assessed at month 3, 6, 9 and 12 visits in all participants, in addition to testing at interim visits, if indicated (e.g. symptomatic). A primary endpoint event is defined as occurrence of any one of the above STIs diagnosed within each quarter, with the exception that repeat diagnosis of the same STI within 28 days of a quarterly visit is assumed to be the same infection (i.e. not an incident infection). Any infection diagnosed at an interim visit (outside the 28 days) will be counted as a primary endpoint for that quarter i.e., if a participant is diagnosed with GC

at 40 days after their 6 month visit, this will be analysed as a primary 9 month endpoint. All endpoints will be reviewed by the endpoint adjudication committee, blinded to arm assignment, for final determination, using most current CDC STI guidance.

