A concern about a single post-sex dose of doxycycline is the long *in vivo* doubling time of syphilis (approximately 30-33 hours)^{31, 32}, which is the rationale for treatment of early syphilis with long-acting IM penicillin or oral doxycycline for 14 days. However, the incubation time for syphilis is 10-90 days,³³and doxycycline PEP administered within 72 hours of exposure may deliver sufficient chemoprophylaxis to abort primary infection. Notably, in IPERGAY, a 73% reduction in syphilis incidence was observed with single dose doxycycline.¹ In

addition, single dose doxycycline PEP has been shown to be effective for Lyme disease³⁴ and leptospirosis ^{35, 36} – spirochetal diseases that also have slow doubling times.^{35, 37} An alternative approach is doxycycline PrEP (i.e., daily dosing).²² However, daily doxycycline PrEP may have a higher frequency of intolerability due to side effects, selection of antimicrobial resistance through higher exposure, and greater costs than doxycycline PEP. Importantly, MSM in IPERGAY demonstrated their ability to effectively adhere to peri-coital Truvada PrEP and post-coital doxycycline PEP.

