6.2 Study visits

Specific study procedures are detailed in Table 6.1. Visits will take place at enrollment and quarterly thereafter, up to 12 months. Interim visits may be scheduled for diagnosis and treatment of STI and collection of additional specimens or for evaluation of possible doxycycline associated adverse events. Participants may also request interim STI testing.

6.2.1 Enrollment Visit After confirming eligibility through pre-screening and prior to study procedures, we will obtain written informed consent and collect locating information; the latter will be updated at each study visit. At enrollment, demographic, behavioral, and clinical information will be collected and a release of information obtained to permit access to medical records. STI testing for chlamydia and gonorrhea through nucleic acid amplification testing (NAAT) of clinician or self-collected pharyngeal and rectal swabs and first void urine will be conducted. Serologic testing for syphilis will be conducted. If required STI testing has been conducted within past 30 days, these results may be used for the enrollment evaluation. Participants diagnosed with an STI at baseline will be treated; presence of a baseline STI will not preclude enrollment but STI's present at time of enrollment will not count towards study endpoints. All STIs will be reported to the local health department as required per local standard procedures.

Randomization Within 14 days of enrollment, participants will be randomized in a 2:1 ratio to openlabel doxycycline PEP or the standard of care control condition (regular STI counseling, screening and treatment as indicated). The randomization code and resulting allocation list will be generated and maintained by the study statistician. The list will be blocked and stratified by site. While neither participants nor study staff will be blind to each participant's randomization group once assigned, the randomization scheme will utilize varying block sizes in order to protect the blind prior to randomization of each participant.

- 6.2.2 Quarterly visits after enrollment. Quarterly visits will be conducted every 90 days, +2 weeks/ -10 weeks. Participants unable to attend a quarterly visit will be asked to return for an unscheduled visit as soon as feasible. The quarterly evaluations should be completed at the time of this visit. Subsequent visits should occur on the assigned quarterly scheduled to the extent possible.

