7.5. Analysis of the Primary Efficacy Endpoint

7.5.1. Primary Efficacy Analysis

The primary analysis of efficacy will be conducted in the ITT cohort.

Endpoint definitions:

Primary endpoint: **Any STI** in the first, second, third or fourth quarter of follow-up, detected in post-baseline testing up to and including STI testing at months 3, 6, 9 and 12. Any STI diagnosed within 28 days of the same STI present at a quarterly visit will not be defined as an incident infection (suggesting incomplete treatment or persistent NAAT positivity without active infection, rather than re-infection). Incident infections detected and treated at interim visits after 28 days will be defined as incident infections for the current quarter. To avoid potential assessment bias, these will be handled in the analysis as if they would have been detected at a scheduled visit (months 3, 6, 9, and 12). Therefore, an STI diagnosed at 40 days after the month 6 visit will be carried forward as a primary event at the next scheduled visit (month 9). If a participant has more than one positive STI (either of the same or different bacterial infections at a scheduled visit) it will be counted as one primary event for that quarter. If scheduled visits are missed, infections will be assigned to the next scheduled visit.

All endpoints will be reviewed by the endpoint adjudication committee, blinded to doxycycline PEP assignment, for final determination, using most current CDC STI guidelines.

The criteria for an incident syphilis case will include a four-fold increase in non-treponemal titers (e.g., the RPR) and/or a consistent clinical presentation (e.g., characteristic chancre in primary syphilis which would be confirmed by a darkfield or reactive RPR without the requirement for a four-fold increase in titer).

Descriptive analysis

- The number of participants with any bacterial STI, and with each type of STI, will be summarized at each scheduled visit by arm.
- The number of STIs reported by each participant will be summarized at each scheduled visit by arm.
- For CT and GC, the anatomical site of infections will be detailed.

Statistical analysis

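### Primary endpoints are counted from enrollment rather than randomisation, so some infections that pre-date assignment can enter quarter 1 and modestly dilute the effect

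*SAP*

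**What the plan says.** - SAP 2.2.1.1 starts the count at enrollment: "The primary endpoint is any of the following STI endpoints post-enrollment". SAP 7.5.1 words it as infections "detected in post-baseline testing up to and including STI testing at months 3, 6, 9 and 12" and does not tie baseline to the randomisation date.
- Protocol 6.2.1 separates the two dates: "Within 14 days of enrollment, participants will be randomized in a 2:1 ratio".
- The same section lets the entry test pre-date enrollment: "If required STI testing has been conducted within past 30 days, these results may be used for the enrollment evaluation".
- It also states the intent on prevalent infection: "presence of a baseline STI will not preclude enrollment but STI's present at time of enrollment will not count towards study endpoints".
- The only exclusion in the SAP's counting rules concerns repeat diagnoses: "Any STI diagnosed within 28 days of the same STI present at a quarterly visit will not be defined as an incident infection". It does not address a first diagnosis made before assignment.
- On visit timing, Protocol 6.2.2 says: "Quarterly visits will be conducted every 90 days, +2 weeks/ -10 weeks". The month-3 visit may therefore fall as early as day 20.
- Protocol 1.2.2 notes that "the incubation time for syphilis is 10-90 days".
- SAP 7.5.2 plans three sensitivity analyses: time to first STI, restoring the 28-day repeats, and counting every diagnosis separately.

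**The concern.** Study doxycycline is supplied only after assignment, and Protocol 5.3 limits each dose to 72 hours after sex. It cannot act as post-exposure prophylaxis for an infection acquired well before randomisation. The plan means to keep such infections out, but its rules leave two openings:

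- **The gap.** A positive specimen taken after enrollment and before randomisation satisfies SAP 2.2.1.1 as written.
- **The reused test.** If the entry result is up to 30 days old and nothing is sampled at enrollment, an infection acquired after that result first appears later and looks incident. Blinded adjudication has no sample with which to date it.

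Incubating syphilis is a smaller third route, because even a fresh test can miss it. Events that the drug could not have prevented are added at the same rate to both arms. The estimate then understates the benefit of having doxycycline available, and some power is lost. None of the analyses in SAP 7.5.2 removes these events.

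**Working it through.** **Inputs.** From SAP 3.3.1 and Protocol 10.2: quarterly rates 10% and 5%, ICC 0.2, four visits, 370 evaluable per cohort (246:123), two-sided alpha 0.05. From Protocol 6.2.1 and 6.2.2: gap r of 0 to 14 days, entry-test age g of 0 to 30 days, quarters of 90 days.

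**Step 1: reproduce the plan's power.** The design factor is (1 + 3 × 0.2)/4 = 0.4, so the effective control n is 123/0.4 = 307.5, with 615 on doxycycline.
- The pooled rate is (0.10 + 2 × 0.05)/3 = 0.0667. The null SE is 0.01742 and the alternative SE is 0.01923.
- z = (0.05 − 1.96 × 0.01742)/0.01923 = 0.82, giving power 79.5% against the stated 80%. A log-RR variance gives 80.7%.
- The annual risks also agree: 1 − 0.9⁴ = 34.4% and 1 − 0.95⁴ = 18.5%, against 34% and 19%.

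**Step 2: dilute quarter 1.** Assume constant daily hazards h = −ln(0.9)/90 (control) and h' = −ln(0.95)/90 (doxycycline), with doxycycline acting from randomisation.
- Control quarter 1: 1 − exp[−h(90 + g)].
- Doxycycline quarter 1: 1 − exp[−h(g + r) − h'(90 − r)].
- Quarters 2 to 4 stay at 10% and 5%, and the four quarters are averaged.

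| Every participant has | Q1 control / doxy | Q1 RR | 4-quarter RR | Power, pooled / log-RR |
|---|---|---|---|---|
| no delay | 10.0% / 5.0% | 0.50 | 0.50 | 79.5% / 80.7% |
| r = 14, g = 0 | 10.0% / 5.8% | 0.58 | 0.52 | 75.9% / 76.9% |
| r = 0, g = 30 | 13.1% / 8.3% | 0.63 | 0.54 | 75.1% / 76.1% |
| r = 7, g = 15 | 11.6% / 7.1% | 0.61 | 0.53 | 75.5% / 76.5% |
| r = 14, g = 30 | 13.1% / 9.0% | 0.69 | 0.56 | 71.4% / 72.3% |

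A simpler version, linear in days, agrees: (14 + 346 × 0.5)/360 = 0.52 and (44 + 346 × 0.5)/390 = 0.56. Its log-RR power at both limits is 72.8%.

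**Step 3: partial exposure.** If 25% of participants are at both limits, the four-quarter RR is 0.515 and pooled power is 77.5%.

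**Step 4: counts.** Infection risk over 14 days is 1.6% (about 6 of 370). Over 44 days it is 5.0% (about 19 of 370). Planned events per cohort are 123 × 0.4 + 246 × 0.2 = 98.

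**Step 5: early month-3 visit.** At day 20, the 14-day gap alone gives a quarter-1 RR of 0.85 and a four-quarter RR of 0.525. Both limits together give a four-quarter RR of 0.57.

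**Step 6: quarters 2 to 4 only.** The design factor is (1 + 2 × 0.2)/3 = 0.467 and the effective control n is 123/0.467 = 263.6, giving power of 73.6%.

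**The case against.** The other side has four good arguments.

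- **The protocol already excludes infections present at enrollment.** This stands. A reader might infer that the plan counts, by rule, everything acquired after an old negative test. It does not: infections acquired before enrollment are excluded by intent, and all endpoints go to a blinded committee. What fails is enforcement when an old result is reused. Only the enrollment-to-randomisation gap is a matter of the counting rule itself.
- **The limits are tolerances, not typical values.** This also stands. Protocol 6.1 schedules STI testing and pill dispensing at month 0, which suggests that many gaps are short. Under Protocol 6.8, pre-COVID participants kept their assignment on re-enrollment and so have no randomisation gap.
- **The bias is conservative.** It is the same in both arms by randomisation, and Protocol 1.2.8 reports that the interim analysis crossed its effectiveness thresholds in both cohorts. Nothing here casts doubt on that finding.
- **Changing the wording recovers little.** This is correct as far as it goes. No scheduled test falls in the gap, so the new wording removes only infections detected there, not those acquired there and first found at month 3. It is the reason for adding a second analysis.

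Two further inferences are tempting but unsupported. One is that the 14-day gap inflates the control rate before doxycycline, which is used in Protocol 10.5. With a same-day entry test, control quarter 1 is still 90 days and still 10%. The other is that time to first STI is markedly more affected. Quarter 1 holds 10/34.4 = 29% of control first events and 5/18.5 = 27% of doxycycline first events, against 25% with equal weighting, so the difference is small.

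**Conclusion.** The concern holds as a modest dilution that is cheap to reduce. The SAP's start of counting does not match the date of assignment, and no planned analysis shows how much this matters. With a true RR of 0.50, the four-quarter RR lies between 0.50 and about 0.56, and power between the stated 80% and about 71-73%. The gap alone reaches at most about 0.52 and 76-77%. With a true 65% reduction, both limits together move the RR from 0.35 to 0.425 and power from 96% to 92%.

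These values assume a constant hazard, no treatment or clearance of pre-assignment infections, an immediate drug effect at randomisation, and a month-3 visit at day 90. An earlier visit gives a slightly larger bias (0.57 at day 20). The documents do not say how many participants had a delayed randomisation or a reused test, so the true effect may be close to none. The distortion falls mainly in quarter 1, is towards the null and does not raise type I error.

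**What to change.** 1. **SAP 2.2.1.1 and 7.5.1:** count STIs from specimens collected after randomisation, or after re-enrollment for the pre-COVID participants who kept their assignment. Class any STI with a specimen date on or before that date as baseline. Report by arm how many events this reclassifies.
2. **SAP 7.5.2, time to first STI:** start the clock at the same date.
3. **SAP 7.5.2, new sensitivity analysis:** repeat the primary model on quarters 2 to 4, so that the month-3 test acts as a common clearing test on the assigned arm. This reaches infections acquired before assignment but first found at month 3, which item 1 cannot.

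SAP 1 allows revision before database lock. The work is a wording change and one re-run of the primary model, using dates the trial records should already hold. A few early events leave the primary count. The quarters 2 to 4 analysis has about a quarter fewer observations and about 74% power, so it should be read for consistency of the estimate and not as a second test.

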2.2.1.2. Impact of doxycycline on TCN resistance

1. Resistance of GC to TCN detected in positive GC cultures. Those with positive GC NAAT results will have a swab obtained from the involved anatomic site and other sites of sexual contact in past 90 days (to include throat, rectum, urine) for GC culture-based phenotypic testing. Swabs for GC culture will be collected at time of suspected GC or in patients recalled after positive GC NAAT result reported.
2. Tetracycline resistance detected in *S. aureus* culture-positive nasopharyngeal swabs, collected at baseline, six, and 12 months

2.2.2. Secondary Endpoints

2.2.2.1. Efficacy of doxycycline for individual STIs

Effectiveness of doxycycline will also be assessed for each of the STIs separately, for both cohort combined, using endpoints as defined above.

2.2.2.2. Safety, tolerability and acceptability of doxycycline PEP

- Safety: All grade 2 and higher hematologic and hepatic laboratory abnormalities, all grade 3 and 4 adverse events judged to be associated with doxycycline (possibly, probably, or definitely related), and all SAEs.
- Tolerability: in person quarterly assessments of discontinuations of doxycycline, discontinuation of PEP, symptom assessment, and self-reported side effects questionnaire at 6 and 12 months by CASI (computer assisted self-interview),

In person assessment by research staff at scheduled visits to include:

- All permanent doxycycline discontinuation and reasons for discontinuation;
- For all temporary doxycycline interruptions ≥ 7 days, reason for interruption; and
- Side effects:
 - o presence/absence of the following symptoms and if present, whether attributed to doxycycline (if taking) by a) participant and b) investigator: rash, sunburn, headache, change in vision, pain with swallowing, diarrhea, nausea, vomiting, abdominal pain, or other.

CASI questions related to tolerability

- At least once in the past 3 months, I did not take doxycycline within 3 days after sex because I wanted to avoid side effects. (Reported using 5-point Likert scale)
- Were there any other reasons that you did not take doxycycline within 3 days after sex? Yes/No (Y/N) and open-ended response if yes is selected.
- In the past 3 months, do you feel that taking doxycycline affected your sexual experience? (Reported using 3-point scale: negative, neutral, positive effect).

• Acceptability: self-reported acceptability questionnaire by CASI for all doxycycline PEP recipients administered at month 6 and 12.

Answer to the following questions, reported using a 5-point Likert scale, unless otherwise indicated

- Doxycycline is easy to take.
- I'm worried that taking doxycycline will cause antibiotic drug resistance. (reverse coded)
- I'm worried that doxycycline will hurt my body. (reverse coded)
- Taking doxycycline PEP will reduce my condom use. (reverse coded)
- Doxycycline has other good effects for me.
- Taking doxycycline PEP has helped me take my PrEP or ART more regularly.
- A sexual partner has expressed negative feelings about me taking doxycycline. (reverse coded)
- A sexual partner has expressed positive feelings about me taking doxycycline
- Taking doxycycline only when needed after sex and not every day is... (5-point scale from very unacceptable to very acceptable)
- In my community, taking doxycycline to prevent STDs is considered... (5-point scale from very unacceptable to very acceptable)
- I would continue to take doxycycline to reduce sexually transmitted infections if available to me at no cost after the study.
- I would recommend doxycycline PEP to a friend. (Y/N)

2.2.2.3. Sex acts covered by doxycycline PEP

Sex acts covered by doxycycline will be recorded by quarterly CASI assessment and medication reconciliation as well as optional usage of an ongoing smartphone app (Blackbook).

- CASI: Coverage of sexual contacts and accompanying doxycycline use assessed at month 6 and 12 in the doxycycline PEP arm assessed by the following questions:
 - In the past 3 months, I missed taking doxycycline within 3 days after sex at least once. Y/N
 - In the past 3 months, when you have had anal or vaginal/frontal without using a condom the whole time, how often did you take doxycycline PEP within 72 hours after sex? 5-point scale

- In the past 3 months, when you have given or received oral sex, how often did you take doxycycline PEP within 72 hours after oral sex? 5-point scale
- Of the TIMES you had anal sex or vaginal/frontal sex without a condom, how many TIMES did you take doxycycline PEP within 72 hours after sex? Numeric value
- The last time you had anal or vaginal/frontal sex without using a condom the entire time, did you take doxycycline? Y/N
- Of these times you had oral sex, how many TIMES did you take doxycycline PEP within 72hrs? Numeric value
- The last time you had oral sex did you take doxycycline. Y/N
- How many times did you take doxycycline PEP more than 72 hours after anal or vaginal sex?
- How many times did you take doxycycline PEP more than 72 hours after oral sex?

- Quarterly review of doxycycline dispensing and remaining tablets:
 - Number of doxycycline pills returned at each quarterly visit.
 - Bottles of doxycycline dispensed at each visit.
- Smartphone app: Coverage of sex acts by doxy will also be assessed by use of app, which will prompt participants to record all sexual activity (oral, anal, vaginal), use of condoms, and whether doxycycline was taken after qualifying sexual contact (proportion of sex acts covered).

2.2.2.4. Tetracycline resistance

- Molecular markers of resistance for CT
- Molecular markers of resistance to syphilis
- Phenotypic resistance in nasopharyngeal swabs culture positive for *Neisseria*
- Abundance of TCN resistant genes in rectal swabs from MSM/TGW receiving doxycycline PEP (based on total Tet C and Tet M genes detected, normalized for the quantity of bacterial present, not isolated from specific flora)

3. STUDY DESIGN

3.1. Summary of Study Design

Open label randomized clinical trial of doxycycline PEP to reduce bacterial STIs (*N. gonorrhoeae* [GC], *C. trachomatis* [CT], and *T. pallidum* [syphilis]) among MSM/TGW living with HIV (PLWH) or on HIV PrEP. The trial is powered to separately assess impact for MSM/TGW living with HIV and MSM/TGW on PrEP.

Eligible participants randomized 2:1 to doxycycline PEP will receive open-label doxycycline 200 mg to be taken ideally within 24 hours but no later than 72 hours after condomless sexual contact ((receptive anal, insertive anal, vaginal, or oral, or use of shared sex toys).). 200 mg of doxycycline will be taken at most once per 24-hour period regardless of the number of sexual acts occurring during this time period. Sexual activity will be recorded for both arms of the study (doxycycline PEP and control condition) by the participant using a smartphone application that will be adapted for study use; this will enable comparable assessment of risk in the two arms. PEP pill-taking will also be measured by the app to enable assessment of coverage of sex acts by PEP. Sexual activity and adherence will also be assessed in person at quarterly visits.

STI testing will be conducted quarterly from three anatomic sites (pharyngeal, rectal, and urine samples for GC and CT NAAT testing) and blood obtained for syphilis testing, following CDC guidelines for serologic diagnosis of syphilis.

Participants with a positive STI test will return for STI treatment and for swabs of the affected site for resistance testing; culture- and molecular-based for GC and molecular methods for GC, CT and syphilis. Those with signs and symptoms suggestive of syphilis infection and those with a reactive syphilis serologic test that indicates a new syphilis infection will have swabs of any current active lesion (if present) as well as mucosal swabs from the oropharynx to obtain DNA for molecular testing.

To assess tetracycline resistance in a common, sometimes pathogenic bacteria, swabs from the anterior nares and oropharynx will be obtained at baseline, 6 and 12 months to identify *S. aureus* carriers in whom tetracycline resistance will be evaluated. To assess tetracycline resistance that could be transferred to oropharyngeal GC from commensal *Neisseria* species, oropharyngeal swabs will be obtained at baseline and 12 months to evaluate tetracycline resistance in a carrier.

